#### 4.6 Treatment for Early Discontinuation Cases

Patients who withdraw voluntarily or are discontinued by the Investigator will remain eligible for Standard of Care treatment by the Investigator and study staff.

### 5.0 STUDY SCHEMA

Screening	Background Phase Commerical SCS Device			Washout	Investigation Study Phase DISCSS™ SCS Device		
Day 0	Duration 3-5 days			Duration 1-2 days	Duration 3-4 days		
Visit 1	Visit 2		Visit 3		Visit 4		Visit 5

\*Please note that the Screening Visit (Visit 1, Day 0) may be combined with Visit 2 (Initiation of the Background Phase with Commercial SCS Device) upon Principal Investigator discretion and participant agreement. Combining Visit 1 and Visit 2 is contingent on successful verification of eligibility, completion of all screening evaluations, including meeting informed consent requirements.

### 6.0 STUDY PROCEDURES

#### 6.1 Screening (Visit 1)

Potential participants will be identified from the patient population at the investigative sites. The following procedures will be conducted at Screening:

- Informed Consent: Only patients who sign the IRB-approved informed consent form will be permitted to participate in the clinical study. Participants who do not speak English must be provided a copy of an IRB-approved informed consent form in their native language. The original signed copy of the informed consent will be retained in each participant's study file and a copy will be given to the patient to take home for their records. No study-specific procedures will be done prior to the patient providing informed consent.
- Physical Exam
- Medical History
- Conservative Therapy History
- Medication History
- Urine Pregnancy Test (for female participants only)
- NRS Pain Assessments (back, bilateral lower extremities, and overall pain)
- Anatomical Pain Maps (back, bilateral lower extremities, and overall pain)
- Inclusion and Exclusion Criteria Evaluation

At the completion of the screening exam, the Investigator will evaluate the patient for eligibility. If eligible, the patient can be enrolled. Please note that Visit 1 and Visit 2 may be combined if eligibility is verified and all screening evaluations are completed prior to initiating Visit 2 activities.

## **6.2 Initiation of Background Commercial Trial SCS Device Phase (Visit 2)**

During this visit, the following will occur:

- NRS Pain Assessments (back, bilateral lower extremities, and overall pain)
- Anatomical Pain Maps (back, bilateral lower extremities, and overall pain)
- Concomitant Medication Review
- Percutaneous lead implantation under fluoroscopic guidance, per Manufacturer instructions, if applicable. Note: If the subject has existing permanent implanted leads in place, the permanent leads may be used if the subject is undergoing a paradigm shift in treatment that necessitates trialing of the commercial SCS device. In this case the trial leads will not be used.
- Radiographic Imaging of implanted percutaneous trial leads as described in Section 16.4.
- Connection of the external trial leads to the commercial External Pulse Generator (EPG) system per Manufacturer instructions.
- Programming and adjustment of settings for the commercially available trial SCS system per Manufacturer instructions.
- Assessment of Complications, including but not limited to unusual pain or discomfort during the trial stimulation, local skin reactions at the implant site, and complications related to implantation of percutaneous trial leads
- Review of device use instructions during patient's home use, including all pertinent warnings

The duration of the Background Commercial Trial SCS Device Phase is 3-5 days. At the end of the visit they will be scheduled for Visit 3, the planned termination of the Background Commercial Trial SCS Device Phase.

## **6.3 Completion of Background Trial Commercial SCS Device Phase (Visit 3)**

During this visit, the following will occur:

- NRS Pain Assessments (back, bilateral lower extremities, and overall pain)
- Anatomical Pain Maps (back, bilateral lower extremities, and overall pain)
- Assessment of Complications, including but not limited to unusual pain or discomfort during the trial stimulation, local skin reactions or infection at the implant site
- Concomitant Medication Review
- Disconnection of commercial External Pulse Generator (EPG) (note: the percutaneous trial leads are to remain for the DISCSS™ treatment phase).

Participants who are determined by the Investigator to have successfully completed the background therapy with the commercially available SCS and are willing to participate in the investigational trial phase will return to the clinic after a 24-48 hour washout period to receive the investigational DISCSS™ SCS device and begin the Investigational Study Phase.

#### **6.4 Washout Period**

Participants will spend 24-48 hours undergoing a “washout period” between study phases.

During this period, they will be reminded not to increase the usual dosages of any of their prescribed medications, including pain medications. However, they may decrease their pain medications, if desired. All other prescribed medications (i.e., antihypertensives, hypoglycemics, cardiovascular medications, cardiopulmonary medications, membrane stabilizers, etc.) are to continue as usual.

#### **6.5 Initiation of Investigational Study Phase with DISCSS™ SCS Device (Visit 4)**

Participants will return to the clinic at Visit 4 for initiation of a 3-4 day trial period with the investigational DISCSS™ device. During this visit, the following will occur:

- Investigator confirmation of patient eligibility to start the Investigational Study Phase with the DISCSS™ SCS Device
- NRS Pain Assessments (back, bilateral lower extremities, and overall pain)
- Anatomical Pain Maps (back, bilateral lower extremities, and overall pain)
- Concomitant Medication Review
- Assessment of adverse events
- Radiographic Imaging of implanted percutaneous trial leads.
  - If migration of implanted percutaneous leads has occurred, modification of placement by guided fluoroscopy is performed, followed by radiographic confirmation of location of trial implanted leads
  - Note: Percutaneous lead modification of placement is conducted per the package instructions of the percutaneous trial leads in use.
- Connection of the DISCSS External Pulse Generator (EPG) to the percutaneous trial leads following the instructions in Appendix III: DISCSS™ Stimulator System Clinician Use Guide
- Investigator programming of settings for the investigational DISCSS™ SCS device per the instructions provided in Appendix III: DISCSS™ Stimulator System Clinician Use Guide

The subject will be instructed to contact the Investigator in the event of any adverse events with the DISCSS™ SCS device and/or the percutaneous trial leads. The subject will be trained on the information included in Appendix II:

DISCSS™ Patient User Manual and provided a copy of this document. If device complications occur between Visit 4 and Visit 5, the Investigator will follow the instructions provided in Section 8.9. The subject will return to the clinic for an unscheduled visit as described in Section 6.7, and the device complications and/or adverse events will be addressed clinically and per the procedures outlined in the protocol and the DISCSS™ Stimulator System Clinician Use Guide. If indicated, the Investigator will adjust the settings on the DISCSS™ Stimulator System or, if necessary replace the DISCSS™ Stimulator System Clinician Use Guide as outlined in Section 8.9. If the complication cannot be resolved, the subject will be discontinued from the study as described in Section 4.6.

At the end of the visit they will be scheduled for Visit 5, the completion of the Investigational Study Phase and reminded to return to the clinic at this time to complete the trial.

## **6.6 Completion of Experimental Study Phase with DISCSS™ SCS Device (Visit 5)**

Participants will return to the clinic 3-4 days later for Visit 5. During this visit, the following will occur:

- NRS Pain Assessments (back, bilateral lower extremities, and overall pain)
- Anatomical Pain Maps (back, bilateral lower extremities, and overall pain)
- Patient Subjective Evaluation Questionnaire
- Concomitant Medication Review
- Radiographic documentation and archiving of location of implanted percutaneous leads as described in Section 16.4
- Disconnection of investigational DISCSS™ External Pulse Generator (EPG) SCS device as described in Appendix III: DISCSS™ Stimulator System Clinician Use Guide
- Percutaneous lead removal per Manufacturer instructions, if applicable. Note: If the subject has existing permanent implanted leads in place, the permanent leads may remain in place.
- Assessment of adverse events
- Return of device as described in Section 9.0

## **6.7 Unscheduled Visits**

Participants may be seen for unscheduled visits as needed. Any adverse events, device complications and concomitant medication changes that are reported at unscheduled visits should be documented in the study records and entered in the EDC. Adverse event follow up should be completed per Section 10.0 (Safety Reporting).

## **6.8 Study Completion**

The final study visit occurs at Visit 5 of the Investigational Study Phase with DISCSS™ SCS Device. Participants who undergo early discontinuation from the study will have final data collection on the date of withdrawal.

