### **3.2 Primary Endpoints**

The primary effectiveness endpoints for this study will include:

- Pain intensity ratings on a Numeric Rating Scale (NRS); and
- Anatomical Pain Maps demonstrating location of Back Pain, Leg Pain and Overall Pain

The primary safety endpoints for this study will include:

- Incidence of adverse events arising from the DISCSS™ treatment phase
- Incidence of serious adverse events arising from the DISCSS™ treatment phase

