## **4.0 STUDY ENROLLMENT AND WITHDRAWAL**

### **4.1 Inclusion Criteria**

In order to be eligible to participate in this study, an individual must meet all of the following criteria:

- a) Age greater than 21 years and less than 80 years
- b) Has a diagnosis of chronic neuropathic pain of trunk and limbs
- c) Is eligible for a spinal cord stimulation trial of a commercially available SCS trial system. Subjects will be evaluated at the end of the background Commercial SCS Device phase for complications and appropriateness to continue to the investigational phase with the DISCSS™ system. Complications from the background phase with the commercial SCS device may include, but are not limited to unusual pain or discomfort during the trial stimulation, local skin reactions or infection at the implant site.
- d) Has a Back Pain Score of minimum intensity 5.0 on a Numeric Rating Scale (NRS)
- e) Has an NRS Back Pain Score that is greater than both Leg Pain Scores
- f) Is not a candidate for revision surgery
- g) Has completed a minimum of 6 weeks of conservative therapy (physical therapy, anti-inflammatory medications, or similar therapies) with limited or no reduction in back pain
- h) Is willing to adhere to the warnings associated with the DISCSS™ system

- i) Is willing to halt and/or modify the use of all prescription and over-the-counter analgesics per the Investigator's direction during study participation
- j) Is capable of providing written informed consent
- k) Is able to comply with the requirements of study visits, follow-up phone visits and self-assessment questionnaires
- l) If existing permanent implanted leads are in place, the patient must be undergoing a paradigm shift in treatment (e.g. Conventional Sensory SCS to Sub-Perception SCS) that necessitates trialing of the new commercial SCS device.

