## 8.3 Methods to Minimize Risk

Adequate measures have been taken to minimize all of the above risks prior to initiation of a U.S. feasibility clinical study, including proper design specification and review, and preclinical testing.

The study Sponsor will provide appropriate training to each Investigator prior to each site's respective study initiation. Medical professionals will be trained on the selection criteria and protocol for the clinical study prior to their first use of the investigational device. The training will address topics such as the indications and contraindications for the use of the device, management of adverse events, and follow-up care.

Investigators will assess the possible presence of the risks associated with each device during the study treatment and at each follow-up visit by physical examination and participant interview as applicable.

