## **10.0    SAFETY REPORTING**

### **10.1    Overview and Definitions**

All adverse events associated with the DISCSS™ will be recorded and analyzed. Regulations contained in the FDA and ICH Guidelines will be followed in the identification, reporting and analysis of adverse events.

**Adverse Event:** An adverse event (AE) is any untoward medical occurrence, disease, injury, or untoward clinical signs (including abnormal laboratory findings, surgical complications, etc.), whether related or unrelated to the investigational device or its use.

**Anticipated Adverse Device Effect:** Any adverse effect related to the device, which is identified in the protocol prior to study commencement.

**Serious Adverse Event (SAE):** A Serious Adverse Event is an adverse event which:

- Led to a death,
- Resulted in life threatening illness or injury\*
- Resulted in patient hospitalization or prolongation of existing hospitalization,
- Resulted in patient disability or permanent damage or required intervention to prevent permanent impairment/damage
- Led to a congenital abnormality or birth defect

\* NOTE: the term “life-threatening” refers to an event in which the patient was at a risk of death at the time of the event; it does not refer to an event which hypothetically might have caused death if it were more severe.

**Unanticipated Adverse Device Effects (UADE):** An Unanticipated Adverse Device Effect is:

1. Any serious adverse effect on health or safety or any life threatening problem or death caused by, or associated with, a device, if that effect, problem, or death is not identified in nature, severity, or degree of incidence in this protocol; or
2. Any other unanticipated serious problem associated with a device that relates to the rights, safety, or welfare of the patients.

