## 10.3 Reporting Procedures for All Adverse Events

All adverse events occurring during the study, whether or not attributed to the DISCSS™ treatment, observed by the Investigator or reported by the participant, will be recorded on the Adverse Event CRF. After review with the participant by the study site personnel, all adverse events will be documented in the participant’s source document and on the appropriate CRF pages. The following information must be collected:

- Description of event
- Date of onset
- Date of resolution
- Duration
- Severity
- Relationship to the study device
- Action(s) taken
- Outcome(s)

The Sponsor will make the determination of whether event is anticipated or unanticipated.

The participant should be given appropriate care under medical supervision until symptoms resolve. If the adverse event is of such severity in the Investigator's judgment that it warrants withdrawal from the study, the participant should be withdrawn from treatment and the end of study evaluations should be completed and recorded on Case Report Forms.

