#### **10.5 Relationship to Device or Procedure**

The relationship of an adverse event to the study will be graded as follows:

**None:** The adverse event is not associated with the study device use.

**Remote:** The temporal association is such that the study device is not likely to have had an association with the observed adverse event.

**Possible:** This causal relationship is assigned when the adverse event:

- a) Follows a reasonable temporal sequence from device use, but
- b) Could have been produced by the study participant's clinical state or other modes of therapy administered to the study participant.

**Probable:** This causal relationship is assigned when the adverse event:

- a) Follows a reasonable temporal sequence from device use;
- b) Abates upon discontinuation of the treatment;
- c) Cannot be reasonably explained by known characteristics of the participant's clinical state.

**Definite:** This causal relationship is assigned when the adverse event:

- a) Follows a reasonable temporal sequence from device use;
- b) Abates upon discontinuation of the treatment; and
- c) Is confirmed by the reappearance of the adverse event on repeat exposure.

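### No adverse event assessment is scheduled after DISCSS is disconnected, so late-appearing events reach the primary safety rate only if participants volunteer them

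*Protocol*

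**What the plan says.** Section 6.8 fixes the end of participation: "The final study visit occurs at Visit 5 of the Investigational Study Phase". For the others, "Participants who undergo early discontinuation from the study will have final data collection on the date of withdrawal"; Section 4.3 has the stimulator taken off at that point. Section 6.6 places disconnection of the DISCSS generator, withdrawal of percutaneous leads and an adverse event assessment all at Visit 5. In the Section 7.0 schedule, adverse event review is marked at Visits 4 and 5 and nowhere else.

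The first primary safety endpoint (Section 3.2) is "Incidence of adverse events arising from the DISCSS™ treatment phase"; the second is the same for serious events. Neither carries a time window. Section 10.1 adds: "All adverse events associated with the DISCSS™ will be recorded and analyzed". Section 10.3 sets the recording scope as "All adverse events occurring during the study, whether or not attributed to the DISCSS™ treatment". Section 12.0 will report the number of events and the number and rate of subjects affected.

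Two sentences suggest that further contact was expected. Inclusion criterion 4.1(k) reads "Is able to comply with the requirements of study visits, follow-up phone visits and self-assessment questionnaires", and Section 8.3 says "Investigators will assess the possible presence of the risks associated with each device during the study treatment and at each follow-up visit". Sections 6 and 7 contain no phone visit, and nothing after Visit 5.

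**The concern.** The last planned look at safety falls on the day the exposure ends. Section 8.2 names skin infection, spinal infection, nerve damage and tissue inflammation among the events that may be associated with the device. None of these need be apparent on the day a generator is unplugged or a lead is pulled, and a complication of lead removal itself has no scheduled later look at all.

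The primary safety result is the proportion of participants with an event. If someone develops a related event a week after Visit 5 and does not call the site, that person is counted as event-free. In a feasibility study whose safety data will inform later work with the device, a reassuringly low rate that partly reflects when observation ended would be misleading. The visit schedule belongs to the protocol: an analysis plan can define a counting window, but it cannot create a contact that never took place.

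**Working it through.** The protocol gives no precision or power figure for safety, so there is none to reproduce. The check is a reading of the schedule followed by simple arithmetic.

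**Scheduled observation (Sections 5.0, 6.6, 6.8, 7.0)**
- On DISCSS: 3 to 4 days, Visit 4 to Visit 5.
- After disconnection, completers: 0 days.
- After disconnection, early discontinuers: 0 days, since final data collection is the withdrawal date.
- Percutaneous lead in place: 3 + 1 + 3 = 7 days to 5 + 2 + 4 = 11 days, then withdrawn at the last contact. Of this, 3 + 1 = 4 to 5 + 2 = 7 days come before any DISCSS exposure.

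**Which routes could bring in an event after disconnection?**
- Event already known: Section 10.3 asks for resolution date, duration and outcome; Section 10.6 follows SAEs until they resolve or stop improving; Section 4.3 follows all events to resolution, in the early-discontinuation text. Covered to a good degree.
- New event that the participant reports: Section 6.5 tells participants to contact the investigator, Section 6.7 allows unscheduled visits with entry in the database, and the 72-hour entry rule in Section 10.6 runs from site awareness. Open, with no end date, but passive.
- New event that the participant does not report: no route.

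**What one missed participant is worth**

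With 30 participants on DISCSS (Section 3.1), 1/30 = 3.3 percentage points. Exact (Clopper-Pearson) 95% intervals:
- 0/30: 0%, upper limit 1 − 0.025^(1/30) = 11.6%
- 1/30: 3.3% (0.1% to 17.2%)
- 2/30: 6.7% (0.8% to 22.1%)

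If the study reports 0/30 while one or two participants had a late event, the second or third line is what should have been shown. The range of 0 to 2 missed is assumed.

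**Sensitivity, on assumed inputs only**

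Let p be the true share of participants with a related event and f the share of those whose event starts by disconnection. If late events are not volunteered, the chance of seeing at least one in 30 is 1 − (1 − p·f)^30. With p = 5%:
- f = 1: 1 − 0.95^30 = 78.5%
- f = 0.5: 1 − 0.975^30 = 53.2%
- f = 0.25: 1 − 0.9875^30 = 31.4%

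The protocol gives neither p nor f. These lines show only that the result is sensitive to f.

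**The case against.** The strongest reply is that nothing in the protocol closes adverse event recording at Visit 5. Section 6.8 speaks of the final visit. The instruction to call, the unscheduled visits and the site-awareness rule have no end date, and Section 10.1 supports entering a late report. This stands. A reader might infer that collection stops at Visit 5 for every participant; the text does not say so, and for early discontinuers the relevant date is withdrawal. What ends is scheduled, active enquiry. It is also unclear whether a report two weeks later still falls within the scope of Section 10.3, which is limited to events during the study.

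A second reply is that the endpoint can be read as covering only events of the Visit 4 to Visit 5 phase. That reading is possible. It sits less easily with Section 10.1, and it leaves the phone visits of 4.1(k) without a purpose. Showing later-onset events separately respects both readings.

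Third, late events will be hard to attribute. The leads come from the commercial system, they have been in place 4 to 7 days before DISCSS begins, and other stimulation may have followed. This is true and limits what a call can prove, but it argues for recording those circumstances rather than for not asking.

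A reader might also infer that events still ongoing at Visit 5 can be graded no higher than Possible, because Section 10.5 requires for the two higher grades that the event "Abates upon discontinuation of the treatment". The documents do not support this: Section 10.3 collects resolution date and outcome, Section 10.6 follows SAEs, and nothing freezes the grade at Visit 5.

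**Conclusion.** The gap is real and modest: scheduled safety observation after disconnection is 0 days for completers and early discontinuers alike, the endpoint has no stated window, and the phone visits presupposed by 4.1(k) are missing from the schedule. The reported AE and SAE rates may be too low, by 3.3 points for each participant of 30 whose only related event appears late and goes unreported. How many that would be cannot be estimated from the documents, which give no onset times for the risks in Section 8.2.

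It would go too far to say that the rate can only err low. Events are recorded whatever their cause, so the rate may also contain events that DISCSS did not produce. The omission itself pushes downward; the net error is unknown.

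This is a cheap improvement to a descriptive feasibility study, not a flaw that invalidates it.

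**What to change.** Add to Sections 6.8 and 7.0 one adverse event phone contact for every participant in whom DISCSS was connected, including those who discontinue early, at a single fixed interval after disconnection. The sponsor should choose the interval; 2 to 4 weeks is an example. At the call:
- ask for new events, and for the outcome of any that were ongoing at disconnection;
- record any other stimulation or treatment started before the onset of a new event.

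Report events with onset after disconnection that are graded at least possibly related, separately from events with onset by disconnection. State this window with the endpoint in Section 3.2. The call would also supply the phone visit that 4.1(k) already asks participants to accept.

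Cost: at most 30 calls, one schedule column, one short eCRF page and a sentence or two of text, with no extra clinic visit or procedure. The downside is that each participant's last contact moves later by the chosen interval, and that a longer interval leaves more room for other causes when a late event has to be attributed.
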